### **Dose Modification and Toxicity Management of Infusion Reactions Related to Pembrolizumab Monotherapy, Coformulations or IO Combinations**

Pembrolizumab monotherapy, coformulations or IO combinations may cause severe or life-threatening infusion reactions including severe hypersensitivity or anaphylaxis. Signs and symptoms usually develop during or shortly after drug infusion and generally resolve completely within 24 hours of completion of infusion. Dose modification and toxicity management guidelines on pembrolizumab monotherapy, coformulations or IO combinations associated infusion reactions are provided in [Table 4](#).

Table 4 Pembrolizumab Monotherapy, Coformulations or IO Combinations Infusion Reaction Dose Modification and Treatment Guidelines

NCI CTCAE Grade	Treatment	Premedication at Subsequent Dosing
Grade 1 Mild reaction; infusion interruption not indicated; intervention not indicated	
 
• Increase monitoring of vital signs as medically indicated until the participant is deemed medically stable in the opinion of the investigator
 
	
 
• None
 

Grade 2 Requires therapy or infusion interruption but responds promptly to symptomatic treatment (eg, antihistamines, NSAIDs, narcotics, IV fluids); prophylactic medications indicated for $\leq 24$ hrs	
 
• Stop Infusion
 
• Additional appropriate medical therapy may include, but is not limited to:               
 
○ IV fluids
 
○ Antihistamines
 
○ NSAIDs
 
○ Acetaminophen
 
○ Narcotics
 
 
 
• Increase monitoring of vital signs as medically indicated until the participant is deemed medically stable in the opinion of the investigator.
 
• If symptoms resolve within 1 hour of stopping drug infusion, the infusion may be restarted at 50% of the original infusion rate (eg, from 100 mL/hr to 50 mL/hr). Otherwise dosing will be held until symptoms resolve and the participant should be premedicated for the next scheduled dose.
 
• Participants who develop Grade 2 toxicity despite adequate premedication should be permanently discontinued from further study drug treatment.
 
	
 
• Participant may be premedicated 1.5 h (<math>\pm 30</math> minutes) prior to infusion of study intervention with:
 
• Diphenhydramine 50 mg PO (or equivalent dose of antihistamine).
 
• Acetaminophen 500-1000 mg PO (or equivalent dose of analgesic).
 

NCI CTCAE Grade	Treatment	Premedication at Subsequent Dosing
Grades 3 or 4 Grade 3: Prolonged (ie, not rapidly responsive to symptomatic medication and/or brief interruption of infusion); recurrence of symptoms after initial improvement; hospitalization indicated for other clinical sequelae (eg, renal impairment, pulmonary infiltrates) Grade 4: Life-threatening; pressor or ventilatory support indicated	
 
• Stop Infusion.
 
• Additional appropriate medical therapy may include, but is not limited to:               
 
○ Epinephrine**
 
○ IV fluids
 
○ Antihistamines
 
○ NSAIDs
 
○ Acetaminophen
 
○ Narcotics
 
○ Oxygen
 
○ Pressors
 
○ Corticosteroids
 
 
 
• Increase monitoring of vital signs as medically indicated until the participant is deemed medically stable in the opinion of the investigator.
 
• Hospitalization may be indicated.
 
• **In cases of anaphylaxis, epinephrine should be used immediately.
 
• Participant is permanently discontinued from further study drug treatment.
 
	
 
• No subsequent dosing
 

Appropriate resuscitation equipment should be available at the bedside and a physician readily available during the period of drug administration. For further information, please refer to the Common Terminology Criteria for Adverse Events v5.0 (CTCAE) at http://ctep.cancer.gov		

### **Other Allowed Dose Interruption for Pembrolizumab Monotherapy, Coformulations, or IO Combinations**

Pembrolizumab monotherapy, coformulations, or IO combinations may be interrupted for situations other than treatment-related AEs such as medical or surgical events and/or unforeseen circumstances not related to study intervention. However, study intervention is to be restarted within 3 weeks of the originally scheduled dose and within 42 days of the previously administered dose, unless otherwise discussed with the Sponsor. The reason for study intervention interruption is to be documented in the participant's study record.

#### **6.6.2 Dose Modification for Investigational Agent Intervention**

See Appendix 6 for details on dose modification for specific investigational agents. If treatment with the investigational agent and pembrolizumab is interrupted or discontinued, treatment with pembrolizumab may continue.

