##### **Attribution of Toxicity:**

When study interventions are administered in combination, attribution of an adverse event to a single component is likely to be difficult. Therefore, while the investigator may attribute a toxicity event to pembrolizumab monotherapy, coformulations, or IO combinations, pembrolizumab monotherapy, coformulations, or IO combinations must be held according to

the criteria in the Dose Modification and Toxicity Management Guidelines for Immune-Related Adverse Events.

In these cases where the toxicity is attributed to pembrolizumab coformulations or IO combinations, re-initiation of pembrolizumab as a monotherapy may be considered after communication with and agreement by the Sponsor.

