### **Holding Study Interventions:**

When study interventions are administered in combination and if the AE is considered immune-related, pembrolizumab monotherapy, coformulations, or IO combinations should be held according to recommended Dose Modification criteria.

If the toxicity does not resolve or the criteria for resuming treatment are not met, the participant must be discontinued from pembrolizumab monotherapy, coformulations, or IO combinations.

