### **Restarting Study Interventions:**

Participants may restart pembrolizumab monotherapy, coformulations, or IO combinations as described below:

If the toxicities do resolve and conditions are aligned with what is defined in the Dose Modification and Toxicity Management Guidelines for irAEs, pembrolizumab monotherapy, coformulations, or IO combinations may be restarted at the discretion of the investigator.

Dose Modification and Toxicity Management Guidelines for irAEs associated with pembrolizumab monotherapy, coformulations, or IO combinations are provided in [Table 3](#).

Table 3 Dose Modification and Toxicity Management Guidelines for Immune-related Adverse Events Associated with Pembrolizumab Monotherapy, Coformulations or IO Combinations

General instructions: 1. Severe and life-threatening irAEs should be treated with IV corticosteroids followed by oral steroids. Other immunosuppressive treatment should begin if the irAEs are not controlled by corticosteroids. 2. Pembrolizumab monotherapy, coformulations or IO combinations must be permanently discontinued if the irAE does not resolve or the corticosteroid dose is not $\leq 10$ mg/day within 12 weeks of the last treatment. 3. The corticosteroid taper should begin when the irAE is $\leq$ Grade 1 and continue at least 4 weeks. 4. If pembrolizumab monotherapy, coformulations or IO combinations have been withheld, treatment may resume after the irAE decreased to $\leq$ Grade 1 after corticosteroid taper.				
irAEs	Toxicity Grade (CTCAE v5.0)	Action With Pembrolizumab Monotherapy, Coformulations or IO Combinations	Corticosteroid and/or Other Therapies	Monitoring and Follow-up
Pneumonitis	Grade 2	Withhold	
 
Administer corticosteroids (initial dose of 1 to 2 mg/kg prednisone or equivalent) followed by taper
 
Add prophylactic antibiotics for opportunistic infections
 
	
 
Monitor participants for signs and symptoms of pneumonitis
 
Evaluate participants with suspected pneumonitis with radiographic imaging and initiate corticosteroid treatment
 

	Recurrent Grade 2, Grade 3 or 4	Permanently discontinue		

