# **7 DISCONTINUATION OF STUDY INTERVENTION AND PARTICIPANT WITHDRAWAL**

## **7.1 Discontinuation of Study Intervention**

Discontinuation of study intervention does not represent withdrawal from the study.

As certain data on clinical events beyond study intervention discontinuation may be important to the study, they must be collected through the participant's last scheduled follow-up, even if the participant has discontinued study intervention. Therefore, all participants who discontinue study intervention before completion of the protocol-specified treatment period will still continue to participate in the study as specified in Section 1.3 and Section 8.11.3.

Participants may discontinue study intervention at any time for any reason or be discontinued from the study intervention at the discretion of the investigator should any untoward effect occur. In addition, a participant may be discontinued from study intervention by the investigator or the Sponsor if study intervention is inappropriate, the study plan is violated, or for administrative and/or other safety reasons. Specific details regarding procedures to be performed at study intervention discontinuation are provided in Section 8.1.9.

A participant must be discontinued from study intervention but continue to be monitored in the study for any of the following reasons:

- The participant or participant's legally acceptable representative requests to discontinue study intervention.
- Any prolonged interruption of study intervention beyond the permitted periods, for irAE management or other allowed dose interruptions, as noted in Section 6.6, require Sponsor consultation prior to restarting treatment. If treatment will not be restarted, the participant will continue to be monitored in the study and the reason for discontinuation of study intervention will be recorded in the medical record.

Note: refer to Appendix 6 for specific investigational agent criteria.

- The participant has a medical condition or personal circumstance which, in the opinion of the investigator and/or Sponsor, placed the participant at unnecessary risk from continued administration of study intervention.

- The participant has a confirmed positive serum pregnancy test.
- Confirmed radiographic disease progression outlined in Section 8.2 (exception if the Sponsor approves treatment continuation).

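### Section 6.6.2 lets pembrolizumab continue after treatment is interrupted or discontinued, with no exception for the mandatory stops and the Sponsor agreement set out in Section 6.6.1

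*Combined protocol and SAP*

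**What the plan says.** All of the following is in the combined protocol and SAP.

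- **Section 6.6.2** points to Appendix 6 for agent-specific rules and then adds: "If treatment with the investigational agent and pembrolizumab is interrupted or discontinued, treatment with pembrolizumab may continue". No condition is attached.
- **Section 6.6.1, Attribution of Toxicity.** Where toxicity is attributed to a pembrolizumab coformulation or IO combination, "re-initiation of pembrolizumab as a monotherapy may be considered after communication with and agreement by the Sponsor".
- **Section 6.6.1, Holding Study Interventions.** If the toxicity does not resolve or the conditions for resuming are not met, "the participant must be discontinued from pembrolizumab monotherapy, coformulations, or IO combinations".
- **Section 6.6.1, Table 3, general instruction 2.** The same three treatment categories "must be permanently discontinued if the irAE does not resolve or the corticosteroid dose is not" at or below 10 mg/day "within 12 weeks of the last treatment".
- **Section 6.6.1, Table 4, Grade 3 or 4 infusion reaction.** "Participant is permanently discontinued from further study drug treatment".
- **Section 6.6.3.** For overlapping toxicities, sites are sent to 6.6.1, 6.6.2 and Appendix 6. If there is no improvement, the investigator is asked to consider stopping the participant.
- **Section 7.1.** In a list of reasons for mandatory discontinuation, one bullet says that interruptions beyond the permitted periods, irAE management included, "as noted in Section 6.6, require Sponsor consultation prior to restarting treatment". Another bullet in that list makes any toxicity that Section 6.6 names for permanent discontinuation a mandatory reason to stop.
- **Section 10.3.5, Assessment of causality.** A planned rechallenge after a serious AE possibly caused by the product, or a re-exposure carrying additional significant risk, needs advance approval from the Sponsor's clinical director.

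**The concern.** A site that holds or stops both drugs for an immune-related event has to know whether pembrolizumab may be given again, and who must agree. Section 6.6.2 appears to answer yes without conditions. Section 6.6.1 answers no in some cases and only with Sponsor agreement in others. Two sites could therefore follow the protocol and treat the same event differently.

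What is at stake is re-exposure after immune toxicity or a severe infusion reaction. The study is open-label and has no data monitoring committee, although Section 8.4.6 says the Sponsor monitors aggregated efficacy and safety data. Consistent application across sites therefore depends largely on the written rules.

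**Working it through.** The point rests on no alpha, power, rate or sample-size figure, so there is nothing to reproduce. The check sets the passages side by side.

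**Step 1. Literal reading of 6.6.2.** The condition names both drugs as interrupted or discontinued. The consequence is that one of them may continue. For an interruption this could loosely mean resumption. For a discontinuation it contradicts itself.

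**Step 2. Charitable reading.** Take the condition to mean that the combination regimen stops and pembrolizumab alone goes on. Then test it case by case:

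| Situation | Section 6.6.1 | Section 6.6.2 | Result |
|---|---|---|---|
| Toxicity does not resolve, or resumption conditions not met | Stop is mandatory and names pembrolizumab monotherapy | May continue | Conflict |
| irAE unresolved, or steroid above 10 mg/day, 12 weeks after last treatment (12 × 7 = 84 days) | Permanent stop, naming pembrolizumab monotherapy | May continue | Conflict |
| Grade 3 or 4 infusion reaction | Permanent stop of study drug | May continue | Conflict |
| Toxicity attributed to a coformulation or IO combination, pembrolizumab alone proposed | Sponsor agreement needed | May continue, no Sponsor step | Condition omitted |
| Interruption unrelated to toxicity | Restart limits of 3 weeks from the scheduled dose and 42 days from the previous one (21 + 21), unless discussed with the Sponsor | May continue | No conflict of substance |

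The charitable reading removes the self-contradiction. Three direct conflicts and one omitted condition remain. The fourth row is likely to be common, because Section 10.3.5 says causality should in general be assigned to the whole combination regimen.

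**Step 3. Does Appendix 6 repair it?** No. Sections 10.6.1.19, 10.6.2.19 and 10.6.3.19 add no dose-modification rule for any of the three agents and refer back to 6.6.1.

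**Step 4. Section 6.6.3.** Toxicity that has not improved has also not resolved. An immune-related event whose attribution between the two drugs is unclear therefore falls under both 6.6.3 (consider stopping) and the holding rule of 6.6.1 (must stop). Section 6.6.3 also brings 6.6.2 directly into the management of such events.

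**Step 5. Section 7.1.** The 12 weeks in Table 3 limits irAE resolution and steroid dose, not the length of the hold. A participant can meet that criterion and still be dosed late, and the consultation bullet can apply there. The separate bullet on permanent discontinuation brings the Section 6.6 rules into the same list. The two can therefore be read together. The text is still unclear on three counts. The consultation bullet names irAE management without excluding cases that Table 3 ends permanently. It allows a restart inside a list of mandatory stops. Nothing says which bullet prevails.

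**The case against.** The strongest defence is that 6.6.2 is loosely worded and other text controls it. Its heading concerns the investigational agent, so the combination reading is natural, and 6.6.1 itself foresees pembrolizumab alone being restarted. A permission does not ordinarily override a mandatory rule, and Section 7.1 repeats the mandatory rules. Section 10.3.5 already requires advance Sponsor approval for rechallenge after serious or high-risk events. The Sponsor agreement in 6.6.1 is confined to toxicity attributed to coformulations or IO combinations. Elsewhere 6.6.1 leaves restart to the investigator once toxicities have resolved and the guideline conditions are met.

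Much of this stands. It is wrong to say that the protocol has no Sponsor step, or that every resumption of pembrolizumab needs Sponsor agreement. But a site has to assemble the answer from five sections, and no sentence says which one governs. Section 10.3.5 does not settle it either: it refers back to the dose-modification guidelines, and it covers only serious or high-risk re-exposure.

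Stronger readings are tempting, and the documents do not support them:

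- **Section 7.1 contradicts Table 3.** It does not, for the reasons in Step 5 of the working.
- **About 4 of 45 participants per arm would be affected.** This takes the 4 of 46 (8.7%) who stopped for an AE in the MK-0482 combination Phase 1 cohort (Section 10.6.3.4). One of those four events was fatal and one was judged unrelated, leaving 2 of 46 (4.3%). That cohort had solid tumours of any type, and its AE stops do not measure how often these passages would collide.
- **The primary analysis or the recording of discontinuations is compromised.** Response is analysed in all treated participants with measurable disease, by assigned arm, so continuing pembrolizumab alone changes nobody's inclusion. The eCRF is not in the documents, so no defect in it can be shown.

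**Conclusion.** Section 6.6.2 is wrong as written. On its literal reading it contradicts itself. On its best reading it conflicts with three mandatory stops in 6.6.1 and omits one Sponsor-agreement condition. Section 6.6.3 adds a weaker instruction where 6.6.1 is mandatory. Section 7.1 is an ambiguity only.

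No number of affected participants can be derived. Table 10 lists all three arms as closed to randomization, so current exposure is limited to participants still on treatment or eligible to resume it. Treatment can last about 2 years. The sentence sits in the main body, so any arm added through Appendix 6 would inherit it. This is a clarification for the next amendment. The conclusion rests on the protocol text alone and assumes that no unseen master protocol text or site instruction sets an order of precedence. It takes no view on which clinical rule is right.

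**What to change.** In the next amendment, reconcile these passages:

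- Section 6.6.1: Attribution of Toxicity, Holding, Restarting, Table 3 general instruction 2, and the Grade 3 or 4 row of Table 4;
- Section 6.6.2: the sentence on continuing pembrolizumab;
- Section 6.6.3: the instruction for toxicity that does not improve;
- Section 7.1: the bullets on prolonged interruption and on permanent discontinuation;
- Section 10.3.5: the rechallenge note.

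After the change, the 6.6.2 sentence should no longer conflict with the discontinuation and Sponsor-agreement rules of 6.6.1. The text should say which passage prevails when two apply, and Section 7.1 should say whether its consultation step reaches cases that Table 3 ends permanently. The sponsor decides which rule stands in each case.

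The cost is a wording change in a few sections. Data collection, analysis and sample size are untouched.

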#### **6.6.3 Dose Modifications for Overlapping Toxicities**

For overlapping toxicities where it is unclear if the event is related to pembrolizumab, the investigational agent(s), or both, it is recommended to hold all drugs and initiate management as outlined in Section 6.6.1, Section 6.6.2, and Appendix 6 (for the investigational agent). If toxicity does not improve, the investigator should consider discontinuing the participant.

## **6.7 Intervention After the End of the Study**

There is no study-specified intervention after the end of the study.

## **6.8 Clinical Supplies Disclosure**

Refer to the master protocol (Protocol 3475-U01) for information on clinical supplies disclosure.

# **7 DISCONTINUATION OF STUDY INTERVENTION AND PARTICIPANT WITHDRAWAL**

## **7.1 Discontinuation of Study Intervention**

Discontinuation of study intervention does not represent withdrawal from the study.

As certain data on clinical events beyond study intervention discontinuation may be important to the study, they must be collected through the participant's last scheduled follow-up, even if the participant has discontinued study intervention. Therefore, all participants who discontinue study intervention before completion of the protocol-specified treatment period will still continue to participate in the study as specified in Section 1.3 and Section 8.11.3.

Participants may discontinue study intervention at any time for any reason or be discontinued from the study intervention at the discretion of the investigator should any untoward effect occur. In addition, a participant may be discontinued from study intervention by the investigator or the Sponsor if study intervention is inappropriate, the study plan is violated, or for administrative and/or other safety reasons. Specific details regarding procedures to be performed at study intervention discontinuation are provided in Section 8.1.9.

A participant must be discontinued from study intervention but continue to be monitored in the study for any of the following reasons:

- The participant or participant's legally acceptable representative requests to discontinue study intervention.
- Any prolonged interruption of study intervention beyond the permitted periods, for irAE management or other allowed dose interruptions, as noted in Section 6.6, require Sponsor consultation prior to restarting treatment. If treatment will not be restarted, the participant will continue to be monitored in the study and the reason for discontinuation of study intervention will be recorded in the medical record.

Note: refer to Appendix 6 for specific investigational agent criteria.

- The participant has a medical condition or personal circumstance which, in the opinion of the investigator and/or Sponsor, placed the participant at unnecessary risk from continued administration of study intervention.

- The participant has a confirmed positive serum pregnancy test.
- Confirmed radiographic disease progression outlined in Section 8.2 (exception if the Sponsor approves treatment continuation).
- Any study intervention-related toxicity specified as a reason for permanent discontinuation as defined in the guidelines for dose modification due to AEs in Section 6.6.
- Completion of 35 treatments of protocol-defined pembrolizumab + investigational agent.

Note: The number of treatments is calculated starting with the first dose.

## **7.2 Participant Withdrawal From the Study**

A participant must be withdrawn from the study if the participant or participant's legally acceptable representative withdraws consent from the study.

If a participant withdraws from the study, they will no longer receive study treatment or be followed at scheduled protocol visits.

Specific details regarding procedures to be performed at the time of withdrawal from the study, as well as specific details regarding withdrawal from future biomedical research, are outlined in Section 8.1.9. The procedures to be performed should a participant repeatedly fail to return for scheduled visits and/or if the study site is unable to contact the participant are outlined in Section 7.3.

